5.2.2 Masking Procedures

This is a partially-blind clinical study as the unadjuvanted A/H3N2v vaccine treatment arm will be open-label to avoid the need for placebo administration at approximately Day 29. Investigators and study personnel will remain blinded to allocation of A/H7N9 with or without AS03.

The randomization scheme will be generated by the SDCC and provided to unblinded study personnel (i.e., research pharmacists performing study vaccination preparations and unblinded study vaccine administrators) at the participating VTEU site.

The unblinded study vaccine administrator is a study personnel member credentialed to administer vaccines and may also participate in dose preparation, but will not be involved in study-related assessments or have subject contact for data collection following study vaccine administration.

Laboratory personnel performing antibody, cytokine\chemokine, and RNA-Seq assays will be masked to A/H7N9 and A/H3N2v treatment groups, subject ID, and study visit for all study specimens. For proteomics assays, A/H7N9 treatment groups and study visit will be masked. Subject IDs will be replaced by random IDs generated by the SDCC to allow proteomics batch-processing of specimens obtained from the same subject. In all cases, the SDCC will generate random specimen picklists for each laboratory to determine which specimens will be tested. After all subjects have completed Day 57, the database will be locked to facilitate data analysis. At the discretion of DMID, unmasking of laboratories may occur after all data have been locked, analyzed and interpreted and the final CSR has been completed.

The Safety Monitoring Committee (SMC) may receive data in aggregate and presented by treatment arm. The SMC may also be provided with expected and observed rates of the expected AEs in an unblinded fashion, and may request the treatment arm be unblinded for an individual

subject if required for safety assessment. The SMC will review grouped and unblinded data in the closed session only.

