11.5.1 Systems Biology Analyses

11.5.1.1 Transcriptomics (RNA-seq)

RNA-Seq data will be pre-processed by removing adapters and low-quality reads and mapping sequences to the latest human reference genome using splice-aware alignment software such as HISAT2.. Gene expression quantification will be carried out by using *Subread* against a common gene model reference. Systematic differences between samples will be normalized using the TMM method as implemented in the *edgeR* R package. Post normalization, genes that are known ribosomal, transfer, and mitochondrial RNA genes or genes located on the X or Y chromosomes will be excluded to avoid gender-specific effects. Moderated log counts per million (LCPM) for the remaining genes will be determined using *edgeR*. LCPM will be used to identify lowly expressed genes, technical bias (e.g. batch effects or GC-content bias), and outlying samples. More specifically, Principal Component Analysis, non-metric multidimensional scaling, and correlation heatmaps based on LCPM will be carried out to identify potential global outliers and batch effects. Negative binomial models as implemented in *edgeR* will be used to determine differentially expressed genes for each endpoint and time point after removal of lowly expressed genes and outliers. If technical bias is detected and the effect is balanced across comparison groups, it will be accounted for by including a covariate as part of the negative binomial models. To compensate for testing multiple genes, p-values will be adjusted for by calculating false-discovery rates (FDR) based on the Benjamini-Hochberg procedure which controls the false positive rate among significantly differentially expressed genes. Genes with a FDR-value < 0.05 and a fold change of greater or equal to 1.5-fold (up or down regulation) will be deemed to be significantly differentially expressed (DE). Baseline responses (fold change in LCPM) of DE genes will be visualized using heatmaps. Unsupervised multiscale bootstrapping will be carried out to identify robust gene clusters with correlated responses (*pvclust* R package). Visualizations of fold change time trends for robust gene cluster will be provided. In addition, higher order organization of DE genes will be investigated using gene set enrichment analysis based on the latest MSigDB and KEGG databases accounting for gene length bias (*goseq* R package). Pathway maps color-coded by treatment effect will be provided for significantly enriched KEGG pathways. Experimentally determined protein-protein interaction networks including known Influenza A-host interactions centered around DE genes will be generated using data from the IntAct database and visualized using *Cytoscape*. Regularized canonical correlation

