3.2. Endpoints

Primary Endpoints

1. Percentage of subjects achieving seroconversion (defined as either a pre-vaccination HAI titer <1:10 and a post-vaccination HAI titer ≥1:40 or a pre- vaccination HAI titer ≥1:10 and a minimum four-fold rise in post-vaccination HAI antibody titer) at approximately 28 days after the second study vaccination (A/H7N9 vaccine, with and without adjuvant).
2. Percentage of subjects achieving seroconversion at approximately 28 days after the study vaccination with A/H3N2v vaccine.
3. Number of differentially expressed genes based on RNA expression as determined by RNA-Seq analysis, in human immune cells at Days 2, 4, 29, 30, 32, and 36 after study vaccination with AS03-adjuvanted and unadjuvanted A/H7N9 vaccine, as compared to baseline assessments performed prior to vaccination (Days -7, 1, and 29).

Secondary Endpoints

1. Plasma measurement of cytokines and chemokines at each study visit, comparing:
 - a. Post-vaccination time points with pre-vaccination time points by treatment arms.
 - b. AS03-adjuvanted influenza A/H7N9 responses to unadjuvanted influenza A/H7N9 responses.
 - c. Influenza A/H3N2v vaccine to unadjuvanted influenza A/H7N9 vaccine.
 - d. Influenza A/H3N2v vaccine to adjuvanted A/H7N9 vaccine.
2. Serologic response to influenza hemagglutinin:
 - a. Percentage of subjects achieving seroconversion (defined as either a pre-vaccination Neut titer <1:10 and a post-vaccination Neut titer ≥1:40 or a pre-vaccination Neut titer ≥1:10 and a minimum four-fold rise in post-vaccination Neut titer) at approximately 28 days after the second study vaccination (A/H7N9 vaccine, with and without adjuvant).

- b. Percentage of subjects achieving seroconversion at approximately 28 days after the study vaccination with influenza A/H3N2v vaccine.
 - c. Geometric Mean Titers of serum HAI and Neut antibody at baseline (Day -7 and 1) and 28 days after influenza A/H3N2v vaccination.
 - d. Geometric Mean Titers of serum HAI and Neut antibody at baseline (Day -7 and 1), and 28 days after both the first and the second dose of influenza A/H7N9 vaccine (with and without adjuvant).
3. Number of differentially expressed genes based on RNA-Seq analysis in human immune cells at Days 2, 4, and 8 after study vaccination, as compared to baseline assessments (Days -7 and 1) after influenza A/H3N2v vaccine.

Tertiary Endpoints

1. Occurrence of solicited local reactogenicity events within 7 days after each study vaccination.

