9.1.2. Gene Expression Quantification and Data Normalization

Gene expression quantification will be carried out on the gene level using the featureCounts function of the Subread software [8]. Reads that overlap with multiple genes or map to multiple genomic locations on the reference genome will be excluded. Known ribosomal, transfer, and mitochondrial RNA genes will be removed from the final read count analysis dataset. In addition, genes located on the X and Y chromosomes will be excluded from the final read count analysis dataset to avoid gender-related biases.

Systematic sample differences in sequencing coverage will be corrected for by calculating scaling factors for each sample using the trimmed mean of M-values (TMM) method [9] as implemented in the edgeR software [10]. TMM-normalized moderated \log_2 counts per million (LCPM) for each gene will be calculated using the edgeR software [10]. As part of this step, a sequencing coverage-scaled count of 0.5 reads will be added to each gene to avoid taking the log of zero. LCPM distributions will be visualized using univariate boxplots and cumulative distribution function (CDF) plots before and after TMM-normalization.

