9.1.3. Global Outlier and Batch Effect Detection

TMM-normalized LCPM will be standardized (z-score: mean=0, variance=1) and LCPM distributions across samples will be inspected for outliers (potential sample mislabeling, experimental error, etc.) and systematic effects (sample ordering, batch processing, etc.) using hierarchical clustering, multidimensional scaling, and principal component analysis (Figure 7). If outlying samples are discovered, corresponding clinical and laboratory metadata will be inspected for abnormalities. Based on these findings, a decision will be made as to whether the respective RNA-Seq observation should be removed from downstream analyses. The decision will be recorded in the CSR. If a noticeable batch effect is observed, unless an imbalance across vaccine groups is observed, the batch effect may be accounted for by adding a batch blocking factor as part of the negative binomial models (see Section 9.2).

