9.2.1. Identification of DE Genes Compared to Pre-First Vaccination

For each post-first vaccination day and study arm, a negative binomial model will be fit to pre- and post-first vaccination read counts. Each model will include coefficients to estimate subject and pre- vs. post-first vaccination effects. The subject effects for estimating subject-specific pre-first vaccination levels will be added to account for paired samples from the same subject. Effects will be parameterized in the design matrix using dummy variables with one variable for each subject and an additional variable for the vaccination effect. For vaccination effects, the value will be set to 1 for post-first vaccination and 0 for pre-first vaccination observations. For each gene, the statistical significance of the post- vs. pre-vaccination effect will be evaluated using a likelihood ratio testing the following hypothesis on the \log_2 scale:

$$H_0: \mu_{\text{post-vaccination}} - \mu_{\text{pre-vaccination}} = 0, H_1: \mu_{\text{post-vaccination}} - \mu_{\text{pre-vaccination}} \neq 0$$

Genes with an absolute fold change (effect size) of ≥ 1.5 compared to pre-first vaccination and FDR-adjusted p-value < 0.05 will be considered to be significantly DE.

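### The RNA-Seq screen for mislabelled samples is neither compared with recorded sex nor read by subject, so a swap between subjects may go undetected

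*SAP*

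**What the plan says.** SAP 9.1.2 counts reads per gene, after which "genes located on the X and Y chromosomes will be excluded from the final read count analysis dataset to avoid gender-related biases". TMM scaling factors and log counts per million (LCPM) come next. SAP 9.1.3 then works on these values: "LCPM distributions across samples will be inspected for outliers (potential sample mislabeling, experimental error, etc". The tools are hierarchical clustering, multidimensional scaling and principal components. A follow-up has one trigger: "If outlying samples are discovered, corresponding clinical and laboratory metadata will be inspected for abnormalities".

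Protocol 11.5.1.1 gives almost the same order. There, "genes located on the X or Y chromosomes will be excluded to avoid gender-specific effects" after normalisation, and then: "Moderated log counts per million (LCPM) for the remaining genes will be determined using" edgeR. Outlying samples are sought on those values. The two documents differ on whether the removal comes before or after normalisation. They agree that it comes before LCPM is computed.

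The models downstream are paired. SAP 9.2.1 states: "The subject effects for estimating subject-specific pre-first vaccination levels will be added to account for paired samples from the same subject". SAP 9.2.2 uses the same form with Day 29 as the reference. Their output is primary endpoint 3, which begins "Number of differentially expressed genes based on RNA expression as determined by RNA-Seq analysis, in human immune cells at Days 2, 4, 29, 30" (SAP 3.2).

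**The concern.** An outlier screen can show a failed library or a wrong cell type. A monocyte library from another healthy adult need not be an outlier among monocyte libraries, so it need not trigger the metadata review. The RSeQC step in SAP 9.1.1 evaluates alignment quality, not identity. Recorded sex is available for every subject (SAP 10.1 and Listing 6), and X and Y expression ties a library to it directly, but the plan does not use that link.

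The pairing is at stake. A library under the wrong subject puts between-subject differences into what the model treats as a within-subject change. With ten subjects per arm, one wrong library affects a tenth of the pairs for that cell type and day. A wrong Day 29 library is worse placed, because SAP 9.1.4 makes it the reference for all three post-second-dose comparisons.

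**Working it through.** The plan states no power, variance or error rate for this endpoint, so there is no figure of its own to reproduce.

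**Number of libraries.** Arm 1 has 5 RNA-Seq visits and Arms 2 and 3 have 8 (SAP 4.5.2), with 10 subjects per arm (SAP Table 1) and 6 cell types (Protocol 8.2.2.2). Complete data give 10 × 5 + 20 × 8 = 210 libraries per cell type, and 210 × 6 = 1,260 in all.

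**Effect of one undetected swap.** The proxy is a paired t-test on the log2 scale.
- From the plan: n = 10 per arm, and a first-dose baseline that combines two libraries.
- Assumed: within-subject SD s = 0.4 log2, a true log2 fold change of 0.8, and p < 0.001 as a stand-in for the false-discovery threshold.
- Varied: the ratio r of between-subject to within-subject variance.

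With no error, each paired difference has variance s² + s²/2 = 1.5s² = 1.5 × 0.16 = 0.24.

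If two subjects' post-vaccination libraries in the same arm and on the same day are exchanged, the two errors are equal and opposite. The mean fold change does not move. The expected sum of squares rises by 4rs², and on 9 degrees of freedom the variance is multiplied by 1 + 4r/(9 × 1.5). For r = 0.25, 1 and 2 this is 1.07, 1.30 and 1.59.

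If one subject's post-vaccination library is replaced by a foreign one with the same response, the expected factor is 1 + 2r/(10 × 1.5), or 1.03, 1.13 and 1.27.

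Simulated power:

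| Between/within variance ratio | No error | One same-arm exchange | One foreign library |
|---|---|---|---|
| 0.25 | 64% | 60% | 62% |
| 1 | 64% | 50% | 57% |
| 2 | 64% | 42% | 52% |

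If the foreign library carries no response, which is the worst case of a swap across arms, the mean log2 fold change falls by a tenth, from 0.80 to 0.72, and power is about 35%.

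**What a sex check would find.** With m subjects of one sex among 30, the share of random between-subject pairs that are of opposite sex is 2m(30 − m)/(30 × 29). The sex split is not in the documents, so m is varied:
- m = 6: 288/870 = 33%
- m = 9: 378/870 = 43%
- m = 12: 432/870 = 50%
- m = 15: 450/870 = 52%

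**The case against.** Three stronger readings are tempting, and the documents support none of them.

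**That removing X and Y genes lets swaps through.** Keeping those genes in an outlier plot would expose nothing unless someone compared the plot with recorded sex. The exclusion is limited to the final analysis dataset, so the aligned reads and full counts still hold these genes. The gap is the missing comparison.

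**That swaps are bound to pass unseen.** The variance ratio that makes a swap costly also makes it visible. At r = 2 the expected squared distance between two libraries is three times as large between subjects as within one (2 + 2 × 2 = 6 against 2, in units of within-subject variance). The planned autosomal clustering (SAP Figure 7) could then place a swapped library with its true subject. At a low ratio the swap is harder to see but costs little. This argument stands, with one limit: no rule asks for the plots to be read by subject, so detection is possible but not required.

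**That masking makes relabelling errors likely.** Protocol 5.2.2 masks RNA-Seq staff to subject ID and visit and adds: "In all cases, the SDCC will generate random specimen picklists for each laboratory to determine which specimens will be tested". That describes masking and gives no sign of weak control of identifiers. Handling procedures are in the Manual of Procedures, which is not among the documents.

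It is also fair to object that a paired t-test at a fixed threshold is a rough proxy for negative binomial likelihood-ratio tests with false-discovery control, and that it leaves out the 1.5-fold requirement. Protocol 11.2 calls the study hypothesis-generating, which lowers the stakes.

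**Conclusion.** The point holds as a gap in quality control. The plan sets out to catch mislabelled samples, but its only screen is a global-outlier inspection of autosomal expression, with no comparison against sex or subject. A swap between subjects within a cell type may therefore reach the models for primary endpoint 3.

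If that happens, the main cost is lost differentially expressed genes. A same-arm, same-day exchange leaves the mean fold change unchanged and lowers power from 64% to somewhere between 60% and 42%. One foreign library with the same response lowers it to between 62% and 52%. These figures are conditional on an undetected swap and rest on assumed variances. How often swaps occur is unknown, so the expected loss cannot be stated. The check is worth adding because it costs very little; nothing here shows that the planned results would be wrong.

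**What to change.** In SAP 9.1.2 and 9.1.3:
1. Before X and Y genes are dropped, compare each library's Y-linked and XIST expression with the subject's recorded sex.
2. Read the clustering plots already planned by subject within cell type, and say so in the text.
3. Trace each mismatch through the coordinating center's ID key. Correct the label or exclude the library before the models of SAP 9.2 are fitted and before any results by arm are seen. Record the decision in the study report, as 9.1.3 already requires for outliers.
4. Then drop X and Y genes as planned. The endpoint gene set does not change.

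The cost is one plot and one table from counts that already exist. The sex check misses all same-sex swaps, which are 48% to 67% of random between-subject swaps over the sex splits above (100% minus 52% and 33%). Reading the plots by subject may catch some of these. Neither step identifies swaps between visits of one subject. No variant calling is needed. A genotype-style concordance check would go further, but would first have to be squared with Protocol 14.8, which rules out human genetic tests on stored samples.

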9.1.3. Global Outlier and Batch Effect Detection

TMM-normalized LCPM will be standardized (z-score: mean=0, variance=1) and LCPM distributions across samples will be inspected for outliers (potential sample mislabeling, experimental error, etc.) and systematic effects (sample ordering, batch processing, etc.) using hierarchical clustering, multidimensional scaling, and principal component analysis (Figure 7). If outlying samples are discovered, corresponding clinical and laboratory metadata will be inspected for abnormalities. Based on these findings, a decision will be made as to whether the respective RNA-Seq observation should be removed from downstream analyses. The decision will be recorded in the CSR. If a noticeable batch effect is observed, unless an imbalance across vaccine groups is observed, the batch effect may be accounted for by adding a batch blocking factor as part of the negative binomial models (see Section 9.2).

9.1.4. Pre-Vaccination Transcriptomics Activity

The two pre-first vaccination time point RNA-Seq samples (Day -7 to -1 and Day 1) measure the baseline transcriptomics activity for each subject enrolled in this study. For each subject, baseline transcriptomic activity will be represented by averaging results for the two pre-first vaccination samples by using the sum of the read counts for each gene followed by TMM normalization as described in Section 9.1.2. Globally outlying Day -7 to -1 or Day 1 RNA-Seq samples will be excluded (see Section 9.1.3). The combined pre-first vaccination sample will be used as a reference to assess transcriptomics responses at Days 2, 4, 8, or 29 post-first vaccination. The Day 29 time point RNA-Seq sample also measures the pre-second vaccination transcriptomics activity for each subject enrolled in this study. This sample will be used as a reference to assess post-second vaccination responses (Days 2, 4, and 8 post-second vaccination) for subjects that received a second vaccine dose (Study Arms 2 and 3).

9.1.5. Log Fold Change Calculations

Log₂ fold changes (LFC) per gene for each subject and post-vaccination day will be calculated by subtracting pre-vaccination LCPM values from the respective post-vaccination day LCPM value. Two sets of LFC will be determined to separately assess post-first and post-second vaccination responses:

1. Day 2, 4, 8, or 29 vs. pre-first vaccination (averaged Day -7 to -1 and Day 1 results) LCPM for Study Arms 1, 2, and 3.
2. Day 30, 32, and 36 vs. pre-second vaccination (Day 29) LCPM for Study Arms 2 and 3

9.1.6. Determination of Cut Offs for Filtering Lowly Expressed Genes

Transcriptome-wide LCPM results will be used to identify a suitable minimum LCPM filter cut off to exclude lowly expressed genes excluding outlying samples. Genes with mean normalized expression levels below X log₂ counts per million across all samples (all study arms and time points) will be considered to be lowly expressed and will be excluded from the differential expression analysis. To determine a suitable cut off value for X, reverse cumulative distribution function (RCDF) plots summarizing the percentage of genes that exceeded a certain LCPM cut off will be plotted on the y-axis (Figure 8). The goal is to choose a cut off that retains between 10,000 and 14,000 genes for differential analysis. A default cut off of 1 count per million will be used if the targeted gene coverage is met. The filtered set will be used as input for down-stream transcriptomics endpoint analysis described in subsequent sections.

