14.3 Transcriptomics Data

Figure 6: Multivariate starplots of reference alignment statistics

Each sample is depicted by a star. Each ray represents one of the reference alignments statistics. Ray length is globally scaled so that the respective maximum alignment statistic across all samples is 1 and the minimum is 0. Stars will be color-coded by Study Arm.

[figure not shown]

Figure 7: Multivariate PCA, MDS, and hierarchical clustering plots

Standardized LCPM distributions will be used as input for PCA (A), MDS (B, C), and hierarchical clustering (D, E). For MDS and hierarchical clustering, results will be provided for Euclidean (B, D) as well as 1-Spearman correlation distance (C, E).

[figure not shown]

Figure 8: Reverse empirical cumulative distribution function plots to summarize the percentage of genes that pass a certain average LCPM expression cut off

The x-axis represents the log₂ count per million cut off for identifying lowly expressed genes. The y-axis shows the percentage of all genes with a minimum gene expression level across all study samples that exceeds the respective cut off. The grey box indicates the target range of genes to be selected (between 10,000 and 14,000 genes). The black vertical lines represent the actual cut off that would be selected.

[figure not shown]
[figure not shown]

Figure 9: MA and Volcano plots

[figure not shown]
The y-axis on the MA plot (left panel) represents the \log_2 fold change for the respective treatment effect. The x-axis shows the average \log_2 expression level. The y-axis on the Volcano plot (right panel) represents the $-\log_{10}$ adjusted p-value and the x-axis the \log_2 fold change for the respective treatment effect. Each black dot represents a gene. In red: DE genes. Blue dashed line: fold change cut off. MA and Volcano plots will be generated for each post-vaccination day, study arm, and study arm comparison.

Generate MA and Volcano plots for each post-first vaccination day (Day 2, 4, 8 or 29), Study Arm (Study Arm 1, 2, or 3), and pairwise Study Arm Comparison (1 vs. 2, 1 vs. 3, or 2 vs. 3). Repeat for post-second vaccination time points (Day 30, 32, and 36) relative to pre-second vaccination for Study Arms 2 and 3.

Figure 10: DE gene overlap between post-first vaccination days (Study Arm 1, Day 2-29 post-first vaccination)

[figure not shown]

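### The expression filter in SAP 9.1.6 averages over all arms and visits, so a gene induced in one arm at only one or a few visits can be dropped before it is tested

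*SAP*

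**What the plan says.** The third primary endpoint in SAP 3.2 is a count: "Number of differentially expressed genes based on RNA expression as determined by RNA-Seq analysis", for the two A/H7N9 arms at six post-vaccination days. The matching count for A/H3N2v is a secondary endpoint.

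SAP 9.1.6 sets which genes can enter that count. Genes whose mean normalized expression lies below X log2 CPM "across all samples (all study arms and time points) will be considered to be lowly expressed and will be excluded from the differential expression analysis". Two rules fix X: "The goal is to choose a cut off that retains between 10,000 and 14,000 genes for differential analysis", and "A default cut off of 1 count per million will be used if the targeted gene coverage is met". The filtered gene set feeds all later transcriptomic analyses. Zero counts do not enter as minus infinity, because under SAP 9.1.2 "a sequencing coverage-scaled count of 0.5 reads will be added to each gene to avoid taking the log of zero".

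SAP 9.2 then calls a gene differentially expressed if its fold change is at least 1.5 and its FDR-adjusted p-value is below 0.05.

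The Figure 8 legend in SAP Appendix 2 describes the cut-off plot in these words: "The y-axis shows the percentage of all genes with a minimum gene expression level across all study samples that exceeds the respective cut off". The title of the same figure refers to an average LCPM cut-off.

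A separate filter in SAP 9.1.2 acts on chromosome: "genes located on the X and Y chromosomes will be excluded from the final read count analysis dataset to avoid gender-related biases". Protocol 11.5.1.1 states the same exclusion.

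**The concern.** The study looks for responses that belong to a particular arm and a particular day. A filter that averages over all arms and days works against genes with that pattern: the few samples in which the gene is on are outweighed by the many in which it is off. On the log scale the outweighing is severe, because a gene that is off contributes a large negative value.

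Such a gene is removed before any model is fitted. It cannot appear in Tables 126 to 128, in the clusters or in the pathway analyses, and the reported count does not show that it was never tested. The primary count would then be too low, most of all for arms and days whose response is specific.

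**Working it through.** **Inputs.** Ten subjects per arm (SAP 4.1). RNA-Seq visits from SAP 4.5.2: five in Arm 1 (Days -7, 1, 2, 4, 8) and eight in each of Arms 2 and 3 (Days -7, 1, 2, 4, 29, 30, 32, 36). Default X is 1 CPM, which is 0 on the log2 scale. The documents give no figure for the filter's effect that could be reproduced, and the 10,000 to 14,000 target cannot be checked without expression data.

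**Samples per cell type, complete data.** N = 10 × 5 + 20 × 8 = 210. If the two baselines are merged as in SAP 9.1.4, N = 10 × 4 + 20 × 7 = 180. One arm at one visit is 10/210 = 4.8%, or 10/180 = 5.6%. SAP 9.1.6 does not say that the filter is set per cell type. Pooled over six cell types, one arm-visit in one cell type would be 10/1,260 = 0.8%.

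**Level needed to pass.** Let the gene sit at *off* CPM in N − k samples and at *on* CPM in k samples. For the mean log2 CPM to reach X:

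log2(on) − log2(off) = (N/k) × (X − log2(off))

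For the mean on the CPM scale to reach 1: on = (N − (N − k) × off)/k.

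With off = 0.5 CPM, X = 0 and N = 210:

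| Induced in | k | Log2 scale | CPM scale |
|---|---|---|---|
| one arm, one visit | 10 | 2^(200/10) = 1,048,576 CPM | (210 − 100)/10 = 11 CPM |
| one arm, two visits | 20 | 2^(190/20) = 724 CPM | (210 − 95)/20 = 5.75 CPM |
| one arm, four visits | 40 | 2^(170/40) = 19 CPM | (210 − 85)/40 = 3.1 CPM |

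One million CPM is the whole library. With merged baselines the single-visit figure is 2^(170/10) = 131,072 CPM.

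**Genes nearer the cut-off (one arm-visit, log2 scale, N = 210).** Off at 0.75 CPM: 315 CPM, or 420-fold. Off at 0.9 CPM: 8.2 CPM, or about 9-fold.

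**Silent genes.** Sequencing depth is not stated. Assuming 5 to 50 million reads, a zero count is log2(0.5/5) = −3.3 to log2(0.5/50) = −6.6. At 20 million reads the floor is −5.3, and a gene at 1,000 CPM in one arm-visit has a mean of −5.32 + (9.97 + 5.32) × 10/210 = −4.6. It is dropped at X = 0.

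**Tuning X.** The formula depends only on the gap between X and log2(off). For one arm-visit, a gene half a log2 unit below X needs 2^(21 × 0.5) = about 1,450-fold, whatever X is. Moving X changes which genes are affected, not the shortfall.

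**Would the planned model find them?** The paired negative binomial likelihood-ratio test of SAP 9.2.1 was simulated with 10 pairs, subject effects and a merged baseline. Assumed inputs: 10 to 20 million reads, dispersion 0.1 to 0.4 (treated as known), between-subject log SD 0.3, 200 replicates, p < 0.0001. Power was about 100% for 0.05 to 2 CPM and for 0.5 to 5 CPM. For 0.5 to 2 CPM it was 58.5% at dispersion 0.4 and 100% at 0.1. At the default X, a gene with any of these three patterns in a single arm-visit is filtered out under either averaging scale.

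**The case against.** **The single-visit figure is a worst case.** This stands. AS03 is given on Days 1 and 29, and a gene that responds on Day 2 may respond again on Day 30. The requirement for a 0.5 CPM gene then falls from about 1,000,000 to about 724 CPM, and to about 19 CPM if the gene is also on at Days 4 and 32. Even 19 CPM is a 38-fold induction. A reader might infer that the filter removes the main AS03 signature. The documents do not say which genes make up that signature or how they are expressed at rest, so this is not supported.

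**X is only a default.** True, and at X = 0.5 CPM the 0.5 CPM example would pass with no induction. The same shortfall then falls on genes below the new cut-off.

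**The study is hypothesis-generating, and the filter ignores labels.** Both are right (Protocol 11.2; SAP 9.1.6). A label-blind filter does not inflate the FDR, and nothing here suggests false positives. The cost is in sensitivity.

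**Figure 8.** A reader might take its legend as a second, stricter rule that requires every sample to pass. The title says average, and SAP 9.1.6 itself uses the word minimum for the threshold. The legend is loosely worded; it is not another rule.

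**X-linked genes.** A reader might infer that excluding them has no function. The models do carry subject effects: "The subject effects for estimating subject-specific pre-first vaccination levels will be added to account for paired samples from the same subject". A constant sex difference in level therefore cancels. In simulation, a 4-fold difference left the rejection rate at 4.7%, against 5.1% without it. A sex difference in response does not cancel, though this is equally true of the autosomal genes that are kept. The exclusion also has a use in the unpaired outlier checks of SAP 9.1.3. It is disclosed in both documents and is at most a secondary query.

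**Conclusion.** The point holds for the expression filter. On the log2 scale that SAP 9.1.6 specifies, a gene well below the cut-off elsewhere and induced in one arm at one visit cannot realistically pass. Induction at two to four visits still requires increases far above the 1.5-fold threshold. Averaging on the CPM scale softens this but does not remove it (22-fold for a 0.5 CPM gene at one visit). The effect is lost sensitivity and a differential-expression count biased low.

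These figures assume complete data, a filter set per cell type and the default X; the relative shortfall does not depend on X. The claim that such genes are detectable rests on assumed depth and dispersion. How many truly responding genes are lost cannot be computed from the documents, so the bias has a direction but no known size. Because the count is a primary endpoint and the change is small, the rule should be revised before analysis.

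**What to change.** In SAP 9.1.6, replace the mean rule. Within each cell type, keep a gene if its CPM is at or above the cut-off in at least as many samples as the smallest available arm-by-visit group. That number is 10 if data are complete. It should be lower after sample exclusions, or if a gene induced in only some subjects is meant to be kept; with a requirement of 10, nine responders would not be enough. Do not use arm or visit labels, so that the filter stays blind. Tune the cut-off to the same 10,000 to 14,000 target, state that this is done per cell type, and make the Figure 8 legend describe the rule used.

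The cost is a short SAP edit and a small code change. Protocol 11.5.1.1 calls for removal of lowly expressed genes but sets no averaging rule, so it does not stand in the way. The tested set will change: some more low-count genes enter the multiplicity adjustment, and holding the target fixed may displace some genes expressed steadily at a low level.

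If the team also wishes to revisit the X-linked exclusion, any change would have to be reconciled with Protocol 11.5.1.1 and should not be made in the SAP alone.
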